3.6. Statistical Analysis of the Research

Descriptive statistics will be used for participants' demographic and clinical characteristics (age, gender, type of scoliosis, Cobb angle, etc.). The study results will be analyzed using the "Statistical Package for Social Sciences" (SPSS) Version 16.0 statistical program. Standard deviation, mean, minimum, and maximum values will be calculated. A 95% confidence interval will be used to evaluate the reliability of the analysis results. The normality of the distribution of variables will be examined using Kolmogorov-Smirnov/Shapiro-Wilk tests and histogram graphs. For comparisons of lumbopelvic rhythm and postural control between the scoliosis and control groups, an independent samples t-test will be used if the data show a normal distribution, and the Mann-Whitney U test will be used if the data do not show a normal distribution. Pearson correlation analyses will be performed for normally distributed data and Spearman correlation analyses for non-normally distributed data to examine the relationships between lumbopelvic rhythm, postural control, pain level, and quality of life in the AIS group. The significance level will be considered to be $p<0.05$.

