- The aim is to examine the relationship between lumbopelvic rhythm and postural control, daily living activities, and quality of life.

Hypotheses;

H1: Lumbopelvic rhythm differs in individuals with AIS compared to healthy individuals.

H2: Lumbopelvic rhythm in individuals with AIS is related to the localization, type, and severity of the curvature.

H3: In individuals with AIS, lumbopelvic rhythm is associated with postural control.

H4: In individuals with AIS, the lumbopelvic rhythm differs in terms of curvature localization, type, and severity during sitting, standing, and walking.

H5: Lumbopelvic rhythm is related to quality of life in individuals with AIS.

3. Research Materials and Methods

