3.1. Location of the Research

Hacettepe University, Faculty of Physical Therapy and Rehabilitation, Movement Analysis Laboratory

3.2 . Timing of the Research

The study begins on May 15, 2025, and ends on November 15, 2026.

3.3. Characteristics of Individuals to be Included in the Study and Sample Size Calculation

The study group will consist of individuals diagnosed with AIS who apply to the Faculty of Physical Therapy and Rehabilitation at Hacettepe University. Participants in the healthy group will be selected using a snowball method from among the relatives of patients or researchers who apply to the Faculty of Physical Therapy and Rehabilitation. The number of individuals to be included in the study will be determined by a power analysis after analyzing the data of 10 individuals diagnosed with AIS and 10 healthy individuals who meet the inclusion criteria.

AIS group inclusion criteria:

Those diagnosed with AIS,
Between the ages of 10 and 18,
Having a Cobb angle greater than 10°,
Pain intensity < 3
Volunteer individuals

Exclusion Criteria:

Male gender,
Body mass index ≥ 30 ,
The presence of additional pathologies affecting the lumbopelvic region (disc herniation, spondylolisthesis, hip dysplasia, rheumatic diseases, etc.),
Chronic pain lasting longer than 3 months,
Lower extremity length difference > 2 cm
Orthopedic or neurological problems affecting the lower or upper extremities.
A history of acute injury,
History of spinal surgery,
Individuals with vestibular pathology or severe balance disorders

Control Group Inclusion Criteria:

Those who have no diagnosed or known illness,
Between the ages of 10-18
Has similar demographic characteristics to the AIS Group.
Volunteer individuals

Exclusion Criteria:

Male gender,
Body mass index ≥ 30
Individuals with acute injury or pain will be excluded from the study.

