3.4. Type of Research (Place an 'X' in the relevant column)

Cross-sectional	X	
Case Studies		
Cohort Studies	Retrospectiv e	
	Prospective	
Qualitative		
Other (write in place of the cross)		

3.5 . Research Methodology

Data collection will be carried out at the Movement Analysis Laboratory of the Faculty of Physical Therapy and Rehabilitation, Hacettepe University.

Participants' demographic data such as gender, age, height, and weight, as well as age at scoliosis diagnosis, age at menarche, and treatment processes, will be collected through individual self-reporting using a structured questionnaire specifically designed for this study. The questionnaire will be explained to each participant before the research process begins, and after obtaining the necessary consent, it will be completed through face-to-face interviews. The data provided by the participants will be used only for research purposes in accordance with confidentiality principles, and data security will be ensured. All data obtained during the study process will be analyzed only by the research team.

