included in the study will be performed using an Inertial Measurement Unit (IMU). Data will be collected using Movella DOT wearable sensors (Movella Inc. , Henderson, NV, USA) at a sampling rate of 60 Hz. IMU sensors will be placed at C7, the thoracolumbar junction, the lumbosacral junction, and the lateral midpoints of both thighs, and secured to the skin with a flexible band. This placement will allow for the acquisition of lumbar and hip movements. The device will be calibrated before measurements begin for each participant . The device's zero point will be determined while participants stand upright barefoot. Participants will be asked to follow a standardized movement protocol. This protocol includes: maximum trunk flexion by leaning forward while standing, maximum trunk extension by leaning backward while standing, maximum right and left trunk rotation while standing, and right and left lateral trunk flexion while standing, as well as standing up and walking. Participants will be asked to repeat each movement 3 times, and the average of the data will be taken (11,12). The movement patterns of the lumbopelvic region will be analyzed using raw data on acceleration and angular velocity obtained from the IMU device .

Postural control will be assessed using the Bertec Balance Check Screener™ strength platform (BP5050 Bertec Co. , Columbus, OH, USA) (13). The participant will be positioned on the platform with their feet parallel to each other and the distance between their feet being half shoulder width (14). In a static stance, the participant will be asked to remain as still as possible on hard and soft surfaces with their eyes open and closed, and the amount of anterior-posterior and right-left postural sway will be determined. Participants will be asked to move forward, backward, right, and left as far as they can on a hard surface with their eyes open and their feet in the same position, without breaking contact between their feet and the platform, and the amount of displacement of the center of gravity forward,

backward, right, and left (stability limits) will be recorded in cm (15,16). Each measurement will be performed 3 times, and the 3rd measurement will be used in the analysis (17). To assess quality of life, the Scoliosis

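### Section 3.6 fixes an unadjusted test for a non-randomised AIS-versus-control comparison, so any systematic age or body-size gap that predicts the outcome would be counted as an effect of scoliosis

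*Protocol*

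**What the plan says.** All references are to the protocol.

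- **Hypothesis.** "H1: Lumbopelvic rhythm differs in individuals with AIS compared to healthy individuals".
- **Test.** Section 3.6: "For comparisons of lumbopelvic rhythm and postural control between the scoliosis and control groups, an independent samples t-test will be used" when the data are normal; otherwise "the Mann-Whitney U test will be used if the data do not show a normal distribution". No covariate, stratum or pairing is named. Demographic variables appear in 3.6 only under descriptive statistics.
- **Source of the groups.** Under 3.3, the AIS group are patients who apply to the faculty. Controls are "selected using a snowball method from among the relatives of patients or researchers".
- **Comparability by design.** Under 3.3, both groups exclude males and a BMI of 30 or more, and both cover ages 10 to 18. Controls must also meet this criterion: "Has similar demographic characteristics to the AIS Group". It names no variable and no tolerance.
- **Data available.** Section 3.5 collects "demographic data such as gender, age, height, and weight, as well as age at scoliosis diagnosis".
- **Scale of one outcome.** Also in 3.5, displacement forward, "backward, right, and left (stability limits) will be recorded in cm". No scaling to body size is stated.
- **Sample size.** Under 3.3, the number of participants "will be determined by a power analysis after analyzing the data of 10 individuals diagnosed with AIS and 10 healthy individuals". No effect size, SD or power is given.

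**The concern.** H1 and the postural-control comparison are observational contrasts between groups that arrive by different routes. In a randomised study a covariate imbalance is due to chance, and the 5% error rate already allows for it. Here a gap can be systematic, and then the error rate does not allow for it.

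Two conditions must hold together: a systematic gap in age or body size remains after recruitment, and that covariate predicts the outcome. If both hold, part of the gap is read as an effect of scoliosis. A larger sample does not help, because the shift stays the same while the standard error shrinks.

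The age range spans eight years of growth and height is not restricted, so there is room for a gap. A distance leaned in cm is the outcome most likely to depend on body size.

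**Working it through.** **Inputs from the protocol.** Unadjusted t-test or Mann-Whitney U; significance at p<0.05 (taken as two-sided). The protocol gives no sample size, gap or correlation, so there is no planned figure to reproduce.

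**Inputs assumed.** n = 20, 40 or 60 per group; covariate gap g = 0.25 or 0.5 within-group SD; within-group correlation r between covariate and outcome = 0.1, 0.3 or 0.5; no true AIS effect. For scale: if age were uniform over 10 to 18, its SD would be 8/√12 = 2.31 years, so a one-year difference in mean age would be 1/2.31 = 0.43 SD.

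**Step 1: shift in the unadjusted difference.** In outcome SD units, shift = g × r. For example, 0.25 × 0.3 = 0.075 and 0.5 × 0.5 = 0.25.

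**Step 2: false-positive rate of the t-test.** Noncentral t with 2n − 2 degrees of freedom and noncentrality g × r × √(n/2). For g = 0.5, r = 0.5, n = 60: 0.25 × √30 = 1.369, which gives 27.4%.

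| Gap (SD) | r | Shift (SD) | n=20 | n=40 | n=60 |
|---|---|---|---|---|---|
| 0.25 | 0.3 | 0.075 | 5.6% | 6.3% | 6.9% |
| 0.25 | 0.5 | 0.125 | 6.7% | 8.6% | 10.4% |
| 0.5 | 0.1 | 0.05 | 5.3% | 5.6% | 5.8% |
| 0.5 | 0.3 | 0.15 | 7.5% | 10.2% | 12.9% |
| 0.5 | 0.5 | 0.25 | 12.0% | 19.7% | 27.4% |

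With g = 0 or r = 0 the rate is 5.0%.

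**Step 3: the Mann-Whitney alternative.** Simulated on a skewed (lognormal) outcome with g = 0.25-0.5 and r = 0.3-0.5, it rejects 5-12%, 6-19% and 7-26% at n = 20, 40 and 60. It gives no real protection.

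**Step 4: a linear model with two covariates.** Where the covariate is measured, acts linearly and is not itself altered by scoliosis, simulated rejection under no effect is 4.8-5.3% over g = 0, 0.25, 0.5 and r = 0.1, 0.3, 0.5 (20,000 runs per setting).

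**Step 5: when the covariate is altered by scoliosis.** Suppose scoliosis shortens standing height while the outcome depends on body size before that loss (r = 0.5, no AIS effect). With an assumed loss of 0.25 SD, a height-adjusted model rejects about 8% / 10% / 12% at n = 20 / 40 / 60; with 0.5 SD, about 14% / 23% / 32%. The unadjusted and age-adjusted tests stay near 5%. Adjusting for height can therefore create the kind of bias it is meant to remove.

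**Step 6: cost of adjusting for nothing.** With uninformative covariates, no gap and a true difference of 0.5 SD, power is 33.5% / 59.3% / 78.2% unadjusted and 32.2% / 58.2% / 77.3% adjusted, a loss of 1.3 / 1.1 / 0.9 percentage points.

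**The case against.** The design already addresses comparability. Both groups are girls of the same age range under the same BMI cap, and controls must be demographically similar, which, given the data collected in 3.5, plausibly covers age, height and weight. Restriction with a similarity criterion is a recognised alternative to adjustment, and nothing in the protocol points to a gap in a particular direction. The upper figures need a 0.5 SD gap to survive that criterion together with a correlation of 0.5 and 40 to 60 per group. An unseen statistical analysis plan could also add an adjusted analysis.

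Much of this stands. It makes the larger figures less likely and keeps the point conditional. It does not remove the point: the criterion has no tolerance, section 3.6 makes no use of it, and the protocol itself names the unadjusted test. Nor is success of the criterion a full answer. With exact matching on a covariate with r = 0.5, a test that ignores the matching rejects only 2.3-2.5% under no effect and has lower power than the adjusted model (62% against 72% at 40 per group for a 0.5 SD difference).

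Three stronger readings are tempting and not supported:

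- A reader might infer that the H1 result will be biased. The protocol gives neither a gap nor any link between body size and lumbopelvic rhythm.
- A reader might infer that any adjusted model holds 5%. Step 5 shows that this fails for height if scoliosis reduces it.
- A reader might infer that controls recruited among relatives invalidate the independence assumption. With half to all controls in sibling-type pairs (intraclass correlation 0.2-0.4, assumed), the t-test rejects 5-8%; links between a control and a patient make it conservative, at 3-5%. The effect is too small and uncertain to require a clustered analysis.

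**Conclusion.** The concern holds in conditional form. The protocol fixes an unadjusted comparison of non-randomised groups although the covariates needed for adjustment are already collected. Any systematic gap in age or body size that survives recruitment and predicts the outcome goes into the AIS effect.

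The size cannot be established from the protocol. Under the assumed inputs it runs from negligible when the correlation is weak to a false-positive rate of about one in four at the far end of the range. The case is strongest for stability limits in cm and open for lumbopelvic rhythm. This should be changed, but the planned comparison is not thereby shown to be wrong. Confidence is medium.

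**What to change.** In section 3.6:

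- Make the group comparison a linear model of each outcome on group, with age and weight as prespecified covariates. Report the adjusted difference with its 95% CI.
- Keep the t-test or Mann-Whitney U as supportive.
- For stability limits in cm, add a height-adjusted model as a sensitivity analysis only, because scoliosis may itself reduce standing height.

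The sample size is still to be set after the 10 + 10 pilot, so the model can be settled before that power analysis.

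The cost is a change of wording and no new data. Power falls by about 1-2 percentage points if age and weight turn out to be uninformative. Adjustment removes only measured, roughly linear imbalance; differences between the two recruitment routes that are not measured remain.
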